## **6 STUDY PARTICIPANTS**

6.1 Inclusion Criteria:

In order to be eligible to participate in this study, an individual must meet all of the following criteria:

- 1) Provision of signed and dated informed consent
- 2) Willingness to comply with the study procedures and confirmed availability for the study duration.
- 3) Over the age of 16
- 4) Self-reported asthma diagnosis and currently receiving treatment
- 5) Must be regularly prescribed one of the following brands of inhaler and have been using it for at least 1-month prior to enrolment:
  - Fostair pMDI (100 mcg Beclometasone/ 6 mcg Formoterol per dose; 200 mcg Beclometasone/ 6mcg Formoterol per dose); Chiesi Ltd
  - Clenil Modulite pMDI (50 mcg, 100 mcg, 200mcg or 250mcg Beclometasone per dose); Chiesi Ltd
  - Trimbow pMDI (87 mcg Beclometasone, 5 mcg Formoterol, 9 mcg Glycopyrronium per dose); Chiesi Ltd

- Seretide Evohaler pMDI (50 mcg Fluticasone/ Salmeterol 25 mcg per dose; 125 mcg Fluticasone/ Salmeterol 25 mcg per dose; 250 mcg Fluticasone/ Salmeterol 25 mcg per dose); GSK UK Ltd.
- Flixotide Evohaler pMDI (50 mcg Fluticasone per dose; 125 mcg Fluticasone per dose; 250 mcg Fluticasone per dose); GSK UK Ltd.
- 6) Access to a smartphone or tablet device and willingness to use it to regularly assess inhaler technique for the study duration.

# 6.2 Exclusion Criteria:

An individual who meets any of the following criteria will be excluded from participation in this study:

- 1) Using a spacer to assist with using their inhaler.
- 2) Prescribed oral steroids for asthma in the preceding 1-month
- 3) Medication is not self-administered
- 4) Treatment for acute asthma in an ICU within the previous 3 years
- 5) Insufficient understanding of spoken and/ or written English (as judged by the researcher).

## 6.3 Recruitment

It is anticipated that 160 patients will need to volunteer to be screened for eligibility in order to reach the target enrolment size of 126.

The study will be publicised through direct mailing to volunteers already on a database kept by Research for the Future (researchforthefuture.org – an NHS backed campaign to help people find out about and take part in research) and via social media forums.

The study will be adopted on to the NIHR clinical research network (CRN) portfolio. We have already been working with the Greater Manchester CRN who have advised how recruitment can work. Via the CRN portal GP practices will be able to participate in publicising the study to their patients who may be eligible. Practices will search their database for patients with asthma who are using one of the relevant inhalers and who have consented to receive information about research studies. Text messages will be sent to these potential participants.

The message to potential participants from any of these sources will contain a link to a website which will have more detailed information about the study and a short set of questions. By answering and submitting the questions along with contact details the participants will be sent a copy of the PIS and will be consenting to be further contacted by the researcher. The researcher will then contact the potential participant and discuss the details of the study, no less than 24h and no more than 1-week following the submission. If the participant is willing an appointment will be arranged where following further discussion the participant will be asked to provide full informed consent.

Informed consent will be obtained through verbal agreement. Participants attending the baseline appointment will be asked to confirm that they have received and read the written information (PIS). If they have not received a copy this will be provided for the participant to read during the appointment. If they request additional time to consider the appointment will be rearranged. The researcher will read through a scripted summary of the study and record answers to specific consent questions. If the participant prefers (for example if they have literacy or language concerns) they will be offered a more comprehensive scripted summary. Any questions the participant has will be answered by the researcher. The researcher will record the answers to the questions and the participant's consent and sign the form in the presence of the participant. A copy of this will be sent to the participant.

These appointments will be held on a virtual platform such as Zoom.

## 6.4 Randomisation:

Once consent has been obtained and baseline data has been gathered, participants will then undergo simple randomisation. Approximately 50% of people will be allocated to each group. Allocation into the study group will be carried out by the dedicated researcher. Prior to the recruitment of the first patient a random sequence of 150 (greater than the number that will ultimately be recruited) will be generated using the website random.org/sequence. Each participant will be allocated the next available number of the randomly generated sequence. If this is an even number the participant will be allocated to care as usual group and if this is an odd number they will be allocated to the intervention group. For those allocated to the intervention group, a Clip-Tone device along with instructions how to download the app will be sent to them by post and a training appointment will be made. Because of the nature of the intervention, it is not possible to blind participants to which group they are allocated to.

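### The researcher role that recruits, consents and scores participants also allocates them from a list made in advance, and the protocol states no allocation concealment

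*Protocol*

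**What the plan says.** Section 6.4 fixes the allocation procedure in some detail:

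- **The list.** "Prior to the recruitment of the first patient a random sequence of 150 (greater than the number that will ultimately be recruited) will be generated".
- **The order.** "Each participant will be allocated the next available number of the randomly generated sequence".
- **The code.** "If this is an even number the participant will be allocated to care as usual group and if this is an odd number", to the intervention.
- **Who allocates.** "Allocation into the study group will be carried out by the dedicated researcher".
- **When.** "Once consent has been obtained and baseline data has been gathered, participants will then undergo simple randomisation".

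The section does not say who runs the generator or who keeps the output. No sealed envelopes, central or web-based release, or independent holder appear in Section 6.4 or elsewhere in the protocol.

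Other sections give the researcher these tasks:

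- first contact with volunteers (Section 6.3: "The researcher will then contact the potential participant and discuss the details of the study");
- arranging the appointment (Section 5.2, Methods);
- judging whether a volunteer's English is sufficient (Section 6.2, criterion 5);
- taking and recording consent (Section 6.3);
- scoring inhaler technique without blinding (Sections 5.2 and 5.3).

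Section 11 names the researcher as a single member of the trial management group.

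**The concern.** Random generation of a sequence and concealment of that sequence are separate protections. The first makes the list unpredictable when it is made. The second keeps it unpredictable to whoever decides that a particular person enters next. The protocol provides the first and is silent on the second, while giving allocation to the role that recruits.

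If the next arm can be known, three things can drift with it, deliberately or not: whether and when a volunteer is contacted and booked, how a borderline English-language judgement falls, and how strictly the baseline technique is scored. The first two are selection bias. The third acts directly on the outcome, because Section 10.1 analyses improvement relative to baseline: a baseline scored slightly low before a Clip-Tone allocation looks like improvement later. None of these can be reliably removed in the analysis.

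The planned difference is small (0.6 points, Section 10.2), so a modest distortion would matter. Allocation procedure also belongs in the protocol, so the gap cannot be put down to a statistical analysis plan that is not shown.

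**Working it through.** **Step 1. Could the next arm be known at each point where the researcher has a choice?**

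| Step | Who acts | Relative to allocation | Is the next arm protected by the text? |
|---|---|---|---|
| Online eligibility questionnaire | Participant | Before | Not needed; participant-driven |
| First contact and booking (5.2, 6.3) | Researcher | Before | No |
| English-language judgement (6.2) | Researcher | Before | No |
| Consent (6.3) | Researcher | Before | No |
| Baseline technique score (5.2) | Researcher | Before, as baseline data | No |
| Allocation (6.4) | Researcher | n/a | List fixed in advance, code open |

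Anyone with sight of the list can read the upcoming arms, because numbers are used in order and the odd/even rule is published in the protocol. Whether the researcher has that sight is not stated. The finding is that nothing excludes it.

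**Step 2. How much discretion is there?** Section 6.3 expects 160 volunteers for 126 places, so about 34 (160 − 126) are screened but not enrolled. Contact may fall anywhere from 24 hours to one week after submission, and a baseline appointment can be rearranged if the volunteer wants more time. The room is limited but real.

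**Step 3. The plan's own figures.** Section 10.2 gives end-of-study means of 9.5 and 8.9, each with SD 1, so the difference is 0.6. Power and sidedness are not stated. Assuming 80% power and a two-sided 5% test:

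n per arm = 2 × (1.96 + 0.842)² × 1² / 0.6² = 43.6, rounded up to 44, or 88 in total. Then 88 / 0.70 = 125.7, rounded up to 126.

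Both stated figures reproduce. Concealment does not alter the sample size.

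**Step 4. Illustration of the consequence (assumed shifts, not in the protocol).** Suppose there is no true effect, but selective entry or baseline scoring shifts the between-arm difference by b points, with SD 1. The two-sided 5% test then rejects with probability

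1 − Φ(1.96 − b/SE) + Φ(−1.96 − b/SE), with SE = √(2/n).

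SE is √(2/44) = 0.213 at 44 per arm and √(2/63) = 0.178 at 63 per arm.

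| Assumed shift b | Share of planned 0.6 | False-positive rate, 44 per arm | False-positive rate, 63 per arm |
|---|---|---|---|
| 0.1 | 17% | 7.6% | 8.7% |
| 0.2 | 33% | 15.5% | 20.2% |
| 0.3 | 50% | 29.1% | 39.1% |

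A larger trial makes this worse, because the bias stays fixed while the standard error shrinks.

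**The case against.** The case on the other side has several parts.

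- **Order of events.** Allocation already follows consent and baseline data. This is a genuine safeguard, but it works only if the next arm is hidden until that moment. With a readable list, the order of paperwork protects little.
- **Limited opportunity.** The first screen is completed by the participant, contact must happen within a week, and only the English-language criterion is expressly left to the researcher's judgement. No eligibility criterion uses the technique or asthma-control score, and both are measured only at the baseline appointment. This stands: when booking or judging English, the researcher has not yet measured the main prognostic variable. It reduces the likely size of selection bias without excluding it, and does not touch the baseline scoring route.
- **Blinded video scoring.** An independent assessor scores the baseline and final videos without knowing the group, so a shifted baseline score could be detected. This partly stands. However, it addresses detection bias rather than who enters which arm. Participants may opt out, and Section 5.3 describes these scores as a check on the researcher's.
- **Change from baseline.** Because improvement is analysed, a pure imbalance in baseline technique would not carry over one-for-one into the effect. This is fair, and is one reason the size is left as an assumption.

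A reader might infer from Section 6.4 that the researcher holds the list and can read off all 126 allocations, or chooses the order of appointments. The protocol says neither: it is silent on who holds the list, and says only that the researcher arranges an appointment. Nor does it support saying that one person controls entry, allocation and outcome, given the blinded scoring of the first and last videos.

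**Conclusion.** The concern holds as a gap in the stated procedure. The protocol gives allocation to the recruiting, consenting and scoring role, from a pre-generated ordered list with an open code, and states nothing that hides the next arm. This rests on reading the researcher and the dedicated researcher as the same role, which the text supports and nowhere contradicts.

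It is not evidence that bias will occur, and no single figure for its size can be defended from the document. The range of about 9% to 39% false positives at 63 per arm (8% to 29% at 44 per arm) depends on assumed shifts of 0.1 to 0.3 points, on SD 1, and on a simple two-sided comparison at 5%. It shows only that small shifts matter against a 0.6-point target.

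**What to change.** Amend Section 6.4 to state that:

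1. The study statistician (Section 11), or another person not involved in recruitment, generates and holds the sequence.
2. The researcher has no access to it.
3. Each allocation is released through the electronic case record system if that system supports it, otherwise through sequentially numbered, opaque, sealed envelopes.
4. Release happens only after eligibility, consent, the baseline technique score and the asthma control questionnaire are saved and locked, with the baseline video too unless the participant has opted out.

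Most of the ordering in item 4 is already in the plan. What is new is the independent holder, the lack of researcher access and the lock.

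The cost is some set-up work, a short amendment and a small delay at the baseline visit. Two practical points need checking: Section 9 describes no randomisation function in the record system, and Section 11 has the statistician attending the management group only when required. The sample size and the allocation ratio do not change.

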6.5 Participants who withdraw consent [or lose capacity to consent]

Participants can withdraw consent at any time without giving a reason, as participation in the research is voluntary, without their care or legal rights being affected.

The investigator may discontinue a participant from the study for the following reasons:

• Lost-to-follow up; unable to contact subject (see Section 7, Lost to Follow-Up)

• Any event or medical condition or situation occurs such that continued collection of follow-up study data would not be in the best interest of the participant or might require an additional treatment that would confound the interpretation of the study

• The participant meets an exclusion criterion (either newly developed or not previously recognised) that precludes further study participation. E.g. if a participant and their healthcare

professional agree to change the participant's device and that is no longer compatible with the Clip-Tone system.

Where given, the reason for participant discontinuation or withdrawal from the study will be recorded on the Case Report Form (CRF).

Where withdrawal or discontinuation occurs at a timepoint before data has been fully anonymised, withdrawing participants may request that all of their data is withdrawn. Where data has been anonymised and it is not possible to withdraw a participant's data this will be communicated to the participant where this is possible.

Subjects who sign the informed consent form, and are randomised but subsequently withdraw, or are discontinued from the study, will be replaced, if the study timetable allows.

# 7 LOST TO FOLLOW-UP

A participant will be considered lost to follow-up if he or she fails to return for 1 scheduled visits and study staff are unable to contact the participant after at least 3 attempts.

The following actions must be taken if a participant fails to return to for a required study visit:

• The site will attempt to contact the participant, reschedule the missed visit within a week, counsel the participant on the importance of maintaining the assigned visit schedule and ascertain if the participant wishes to and/or should continue in the study

• Before a participant is deemed lost to follow-up, the investigator or designee will make every effort to regain contact with the participant (where possible, 3 telephone calls and, if necessary, a certified letter to the participant's last known mailing address or local equivalent methods). These contact attempts will be documented in the participant's study file.

- Should the participant continue to be unreachable, he or she will be considered to have withdrawn from the study with a primary reason of lost to follow-up.
- Should a participant miss a study visit for whatever reason and be unable to reschedule within the timeframe of the visit schedule but wishes to continue in the study, this will be documented in the participant's study file and the following visit will be scheduled as per the study protocol.

## 8 OUTCOME MEASURES

Inhaler technique scores collected at the various time points will be assessed for intra patient differences (whether there is an improvement in an individual over the time period) and inter group differences (whether those using the intervention on average improved more than those

receiving care as usual). Understanding the impact of the intervention on inhaler technique will provide additional evidence to support the wider use of the intervention in clinical practice.

Many studies have previously linked improved inhaler technique with improved asthma control. By assessing whether there are differences in asthma control between the intervention and care as usual groups over the study duration, it may be possible to directly link the intervention with improved disease management. It is important to note that this study is not powered to determine this but exploring this may provide some preliminary data on this issue which may be investigated in the future.

If the results of the study demonstrate a positive outcome in this group of participants, this will provide a foundation to investigate the utility of the intervention in other groups, such as those who use inhalers for COPD.

# 9 DATA COLLECTION, SOURCE DATA AND CONFIDENTIALITY

All data collected will be directly recorded in an electronic clinical record form (eCRF) management system such as Teamscope. All data collected will have a secure audit trail with clear visibility of when, where and who made or modified entries. Data will be encrypted and stored in a cloud-based server which is compliant with GDPR. Any data exported from the eCRF for analysis will be anonymised. The system will also be used to upload the videos and screen captures that will be collected from participants. As soon as they have been uploaded into the eCRF they will be permanently deleted from the device on which it was recorded. Access to the eCRF will be password controlled and access limited to core team members only.

# 9.1 Archiving

Pseudo anonymised source data will be stored for 5 years post publication, after which it will be destroyed.

# **10 STATISTICAL CONSIDERATIONS**

## **10.1** Statistical Analysis

Intention to treat analysis will assess between-group differences in the patient improvement (relative to baseline) in inhaler technique score and inhalation time (at 6 month follow-up). Assessment of in inhaler technique will be done for each visit (1-, 3- and 6-month follow-ups) using parametric and non-parametric tests of differences in distribution location (mean for parametric tests, median for non-parametric tests).

Similar analysis will be performed on a secondary outcome measures – asthma control score (obtained from the ACQ).

More complex analysis, e.g., mixed-effects (multi-level) models, to study the temporal evolution of the primary and secondary outcomes will only be performed if is deemed warranted by the results of the initial between-group analysis.

The proportion of patients in each group at each visit with a correct inhaler technique (achieving maximum score of 10) will be compared within groups over each visit. Comparisons will be made within groups and between groups, using appropriate tests of the follow-up specific 2x2 contingency tables.

We will seek to examine any correlation between frequency of use of the Clip-Tone system in the intervention group to mean inhaler technique scores. Identification of most frequent errors in each group will also be explored (i.e., does CTS have an impact on particular steps?).

We will also intend to carry out per-protocol analysis which will include those participants in the intervention group who used the Clip-Tone Buddy at least once per week in the first month and at least once per fortnight in thereafter. Appropriate parametric and non-parametric tests will be used.

Descriptives of frequency of CTS use and change of use over time will also be carried out. Characteristics of participants who had higher compliance will also examined to identify if the Clip-Tone Buddy app had particular suitability for particular groups of people.

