### Study design

General points:

Although the CTS is currently available (Clip-Tone on prescription and Clip-Tone Buddy app available to purchase on App store) we currently do not know how effective it is in improving and maintaining inhaler technique in patients with asthma. If this data were available, health care professionals would know whether to advise patients to use it. Potentially this is a low-cost solution to a large problem within the asthma community.

In order to gain this evidence, it is important to compare the use of the CTS with "usual care". Some patients will already have good inhaler technique and have adequate education on how to use their inhaler – we do not want to interfere with this and so all patients in the study will continue to see their HCPs as and when they are invited to do so or if the need arises during the study. We will simply ask patients to report what input they have had when we follow them up at each visit. We plan to randomly assign half the participants to the CTS, along with their "usual care" and half to continue with their "usual care" only.

During the Covid pandemic patients have become accustomed to having many of their health consultations performed remotely by video or telephone consultation. The public in general have become used to talking with friends, family, colleagues and having work meetings via Zoom, Microsoft Teams or Facetime. Virtual consultations generally are time saving with no travel time

for participants and easier to fit into our everyday lives. Participants who enter into this study need to have the availability of a mobile smartphone or a tablet in order that they can participate. For these reasons we have planned to carry out the study using virtual consultations. We appreciate that the nature of the study will exclude some members of the public but with smartphone ownership at >90% of all UK under 65-year-olds (OFCOM data 2020) the numbers excluded in this study will be small.

We will reassess recruitment within the first 4-8 weeks of the study and if it is felt participants are being excluded because they want to have face-to-face consultations rather than virtual ones, we will source rooms to see participants and submit an amendment to the protocol and ethics committee.

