## 10.2 Sample Size

To calculate the sample size, we identified previous studies examining interventions to improve inhaler technique. To appropriately power the study to understand if the intervention has a significant impact on improving inhaler technique, or if any improvement observed is as a result of chance (i.e., no significant difference between the intervention and care as usual groups) we will recruit 126 participants. The sample size calculation has been carried out using data from a previous study [20]. In this study, participants had a mean baseline score of 6.8 in both the intervention and control groups. At the end of the study participants in the control group had a mean score of 8.9 (s.d. 1) and the intervention group had a score of 9.5 (s.d. 1). Assuming that the intervention studied here will have a similar impact we calculate a minimum sample size of 88 will be required to power the study to a 0.05 significance level. Recruitment of 126 patients will allow the study to still be adequately powered with up to a 30% drop-out rate. The power calculation takes account of the likelihood that participants in the care as usual group will also be likely to show some improvement in technique.

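### The sample size uses the SD of the end-of-study score but the planned analysis is of improvement from baseline, so the implied 80% power depends on a correlation the protocol does not give

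*Protocol*

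**What the plan says.** Section 10.1 (Statistical Analysis) describes the main comparison this way: "Intention to treat analysis will assess between-group differences in the patient improvement (relative to baseline) in inhaler technique score", with the 6-month visit as the time point. Technique at each visit is to be assessed "using parametric and non-parametric tests of differences in distribution location (mean for parametric tests, median for non-parametric tests". Asthma control is to be handled in a similar way. No baseline covariate is named for either outcome. Mixed-effects models are mentioned for change over time, but they "will only be performed if is deemed warranted by the results of the initial between-group analysis".

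Section 10.2 (Sample Size) takes its inputs from an earlier study in which "participants had a mean baseline score of 6.8 in both the intervention and control groups", and at the end "the control group had a mean score of 8.9 (s.d. 1) and the intervention group had a score of 9.5 (s.d. 1". From this, "we calculate a minimum sample size of 88 will be required to power the study to a 0.05 significance level". Recruitment is set at 126 to allow for up to 30% drop-out. The section states no power, no baseline SD, no SD of change and no baseline to follow-up correlation.

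Under Study design in section 5.2 the protocol also accepts that "Some patients will already have good inhaler technique", and section 6 sets no technique threshold for entry.

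**The concern.** The variable used for sizing and the variable named for analysis are different. The SD of 1 describes how much end-of-study scores vary. The SD of improvement also depends on how much baseline scores vary and on how closely the two scores go together. It can be smaller or larger than 1.

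There is some reason to expect it to be larger. The score has a maximum of 10, the source study's mean was 6.8 at baseline and 8.9 to 9.5 at follow-up, and scores near a ceiling tend to be compressed. A participant who starts at 10 cannot improve, so improvement also depends on the starting score.

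At stake is whether 88 analysable participants are enough for the analysis as described. Section 10.2 says they are, but gives no figure from which this could be checked for improvement scores.

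**Working it through.** **Inputs from section 10.2.** Follow-up means 8.9 and 9.5; SD 1 in each group; baseline mean 6.8 in both; significance level 0.05; minimum total 88; recruitment 126; drop-out up to 30%. Allocation is about 1:1 (section 6.4).

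**Assumptions.** Two-sided test; follow-up SD 1; baseline SD s0 and correlation ρ are not given, so a range is shown. Power is for the two-sample t-test.

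**1. Reproducing the plan's figure.** Difference = 9.5 − 8.9 = 0.6. With 80% power, n per arm = 2(1.96 + 0.8416)² × 1² / 0.6² = 15.70 / 0.36 = 43.6, so 44 per arm and 88 in total. Then 88 / 0.70 = 125.7, so 126. One-sided 80% power would give 70, two-sided 85% would give 100 and two-sided 90% would give 118. The implied design is therefore two-sided with 80% power. The exact t-test power at 44 per arm is 79.5%.

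**2. The difference is the same for improvement.** Equal baseline means give (9.5 − 6.8) − (8.9 − 6.8) = 2.7 − 2.1 = 0.6. Only the SD is in question.

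**3. SD of improvement.** SD_change = √(s0² + 1 − 2ρ·s0). This is at most 1 when ρ ≥ s0/2. In general the condition is ρ ≥ SD_baseline / (2 × SD_follow-up). The break-even is 0.5 for s0 = 1, 0.625 for s0 = 1.25 and 0.75 for s0 = 1.5.

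**4. Power of the change-score test, 44 per arm (the 88 floor).**

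| Baseline SD | ρ = 0.3 | ρ = 0.5 | ρ = 0.7 |
|---|---|---|---|
| 1 | 65% (SD_change 1.18) | 80% (1.00) | 95% (0.77) |
| 1.25 | 54% (1.35) | 68% (1.15) | 87% (0.90) |
| 1.5 | 44% (1.53) | 56% (1.32) | 74% (1.07) |

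If baseline scores varied less than follow-up scores, say s0 = 0.75, power at ρ = 0.5 would be 87%.

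**5. The same test with all 126 analysed (63 per arm, no drop-out).** At s0 = 1, power is 81% (ρ = 0.3) and 92% (ρ = 0.5). At s0 = 1.25 and ρ = 0.5 it is 83%. At s0 = 1.5 it is 59% (ρ = 0.3) and 71% (ρ = 0.5).

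**6. Adjusting the 6-month score for baseline (ANCOVA).** With a linear baseline relation and constant residual variance, the residual SD is √(1 − ρ²), which does not involve s0. At 44 per arm:

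| ρ | Residual SD | Power |
|---|---|---|
| 0 | 1.00 | about 79% |
| 0.3 | 0.95 | 83% |
| 0.5 | 0.87 | 90% |
| 0.7 | 0.71 | 97% |

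The change-score variance exceeds the ANCOVA residual variance by (s0² + 1 − 2ρ·s0) − (1 − ρ²) = (s0 − ρ)², which is never negative. ANCOVA is therefore at least as powerful as the change-score test, apart from the one degree of freedom spent on the baseline term.

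**The case against.** The strongest reply is that a shortfall is not shown. It depends on two quantities the protocol does not give, and the tables have values on both sides of break-even. With equal SDs and a correlation above 0.5, the change-score test has more than the implied power. If few participants drop out, equal SDs and a correlation of 0.3 already give 81%. This stands. A reader might infer that the trial is underpowered, and the documents do not support that. Nor can one say that a stated power is missed, because section 10.2 states none. That baseline scores vary more than follow-up scores is a reasonable expectation from the ceiling, but no figure in the protocol confirms it.

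A second reply is that the choice of covariates is often left to an analysis plan, and that the protocol never calls its test unadjusted. That is partly right: the absence of adjustment is inferred from the tests named, and an unseen analysis plan could add a baseline term. But the protocol does more than leave a gap. It names improvement from baseline as the analysis variable and sizes the trial with the SD of a different variable.

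A reader might also infer that the planned comparison is biased because simple randomisation can leave baseline imbalance. It is not. Under randomisation both the change-score comparison and the adjusted comparison estimate the treatment difference without bias, and chance imbalance is a matter of precision.

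Finally, the gain from ANCOVA should not be overstated. With no correlation it loses a trivial amount (about 79.0% against 79.5%). The cap at 10 also strains the assumptions of linearity and constant variance, so its power figures are approximate.

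**Conclusion.** The mismatch is real and can be read directly from sections 10.1 and 10.2. The 88 reproduces from the end-of-study SD, while the planned analysis is of improvement. The implied 80% power carries over only if the correlation is at least SD_baseline / (2 × SD_follow-up). Over the range in the first table (baseline SD 1 to 1.5, correlation 0.3 to 0.7), power with 88 analysed runs from 44% to 95%, so the claim of adequate power is neither established nor refuted for the planned analysis. These figures assume a follow-up SD of 1, a true difference of 0.6 and a two-sided 5% t-test.

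This is a conditional loss of efficiency, not a threat to validity. It should be fixed, because the remedy removes the dependence on an unknown correlation at almost no statistical cost.

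**What to change.** In section 10.1, state the primary analysis as the between-arm difference in 6-month technique score adjusted for baseline technique score, by ANCOVA or the same terms in a repeated-measures model. Treat the asthma control score in the same way, with its own baseline value as covariate. Show raw improvement descriptively.

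In section 10.2, state the 80% power and the two-sided test, and say that the SD of 1 is that of the follow-up score. Under the adjusted analysis that SD is conservative whenever baseline and follow-up are correlated, and 88 and 126 can stand.

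The cost is wording only. Both baseline measures are already scheduled for every participant, and no extra visits or participants are needed. The change should be made before the data are analysed.
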